3.6. Missing Data and Outliers

3.6.1. Missing Data

In general, missing data will not be imputed unless methods for handling missing data are specified. Exceptions are presented in this document.

Participants with missing outcomes for the primary endpoint due to premature discontinuation from the study will be censored at the Last Study Date defined in Section 3.8.1.

For missing last dosing date of study drug, imputation rules are described in Section 4.2. The handling of missing or incomplete dates for adverse event (AE) onset is described in Section 7.1.5.2, and for prior and concomitant medications in Section 7.4.

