3.8. Analysis Visit Windows

3.8.1. Definition of Study Day

Study day will be calculated from the first dosing date of study drug and derived as follows:

- For assessment dates on or after the first dosing date: Assessment Date First Dosing Date + 1
- For days prior to the first dose: Assessment Date First Dosing Date

Therefore, Study Day 1 is the day of first dose of study drug administration.

Last Dose Date is defined as the maximum, nonmissing, nonzero dose end date of treatment recorded on the Study Drug Administration eCRF form with "Study Drug Permanently Withdrawn" box checked for participants who prematurely discontinued or completed study drug according to the Study Drug Completion eCRF. Refer to Section 4.2 for missing date imputation, if necessary.

Last Study Date is the latest of the study drug start dates and end dates, the in-person or virtual visit dates, the vital sign collection dates, the questionnaire collection dates, the laboratory collection dates, and the death date (if applicable, for participants who died during the study, the death date will be the Last Study Date. For participants who died after completing the study or after prematurely discontinuing the study, the death date will not be considered for the Last Study Date).

Baseline value is defined as the last value obtained on or prior to the first dose date unless otherwise specified (see Section 3.8.3).

3.8.2. **Analysis Visit Windows**

Participant visits might not occur on protocol-specified days. Therefore, for the purpose of analysis, observations will be assigned to analysis windows.

The analysis windows for vital signs are provided in Table 3-1.

Table 3-1.	Analysis Visit V	Vindows for	Vital Signs

		Visit Window Study Day	
Analysis Visit	Nominal Study Day	Lower Limit	Upper Limit
Baseline	1	(none)	1
Day 3	3	2	4*
Day 5	5	4*	7
Day 10	10	8	12
Day 15	15	13	22
Day 29	29	23	34

If the nominal visit is a scheduled visit and the assessment is done on Day 4 (ie, Study Day = 4), assign to Day 3 or Day 5 analysis window based on the nominal visit label. If the nominal visit is an unscheduled visit or early discontinuation visit on Day 4, assign to Day 3 analysis window.

The analysis windows for SARS-CoV-2 mid-turbinate nasal swab are provided in Table 3-2.

		Visit Window Study Day	
Analysis Visit	Nominal Study Day	Lower Limit	Upper Limit
Baseline	1	(none)	1
Day 3	3	2	4*
Day 5	5	4*	7
Day 10	10	8	12
Day 15	15	13	22

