Table 3-2. Analysis Visit Windows for SARS-CoV-2 Mid-turbinate Nasal Swab

* If the nominal visit is a scheduled visit and the assessment is done on Day 4 (ie, Study Day = 4), assign to Day 3 or Day 5 analysis window based on the nominal visit label. If the nominal visit is an unscheduled visit or early discontinuation visit on Day 4, assign to Day 3 analysis window.

The analysis windows for hematology, chemistry, and coagulation laboratory tests are provided in Table 3-3.

Table 3-3.	Analysis Visit Windows for Hematology, Chemistry, and Coagulation
	Laboratory Tests

		Visit Window Study Day	
Analysis Visit	Nominal Study Day	Lower Limit	Upper Limit
Baseline	1	(none)	1
Day 3	3	2	4*
Day 5	5	4*	10
Day 15	15	11	22

* If the nominal visit is a scheduled visit and the assessment is done on Day 4 (ie, Study Day = 4), assign to Day 3 or Day 5 analysis window based on the nominal visit label. If the nominal visit is an unscheduled visit or early discontinuation visit on Day 4, assign to Day 3 analysis window.

The analysis windows for urine or serum pregnancy tests are provided in Table 3-4.

Table 3-4.	Analysis V	'isit Windows :	for Urine or S	Serum Pregnancy Tests
	v			0 1

		Visit Windo	w Study Day
Analysis Visit	Nominal Study Day	Lower Limit	Upper Limit
Baseline	1	(none)	1
Day 15	15	2	22

The Symptoms of Infection with Coronavirus-19 (SIC) questionnaire will be completed daily from predose at Day 1 to Day 15 visit, then at Day 29 visit. Windows are not assigned and results will be summarized for each applicable Study Day through Day 15. For the Day 29 nominal visit, the analysis window is provided in Table 3-5.

		Visit Windo	w Study Day
Analysis Visit	Nominal Study Day	Lower Limit	Upper Limit
Baseline	1	(none)	1
Day 29	29	24	34

Table 3-5. Analysis Visit Windows for the SIC Questionnaire

3.8.3. Selection of Data in the Event of Multiple Records in an Analysis Visit Window

Depending on the statistical analysis method, single values may be required for each analysis window. For example, change from baseline by visit usually requires a single value, whereas a time-to-event analysis would not require 1 value per analysis window.

If multiple valid, nonmissing measurements exist in an analysis window, records will be chosen based on the following rules if a single value is needed:

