6. EFFICACY ANALYSES

6.1. Primary Efficacy Endpoint

6.1.1. Definition of the Primary Efficacy Endpoint

The primary endpoint of the study is the proportion of COVID-19–related hospitalization or all-cause death by Day 29. The endpoint will be derived by combining the available all-cause death and COVID-19–related hospitalization reported by the site.

COVID-19–related hospitalization is defined as \geq 24 hours of acute care for a reason related to COVID-19, in a hospital or similar acute care facility, including emergency rooms or temporary facilities instituted to address medical needs of those with COVID-19. This includes specialized acute medical care units within an assisted living facility or nursing home. This does not include hospitalization for the purposes of public health and/or clinical study execution. The date and duration of hospital admission, and primary reason for hospitalization (including if the hospitalization is related to COVID-19) will be recorded.

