6.1.3. Primary Analysis of the Primary Efficacy Endpoint

The FAPS will be used for the primary efficacy endpoint analysis.

The hazard ratio of COVID-19–related hospitalization or all-cause death by Day 29 between the 2 treatment groups will be estimated using a Cox proportional hazards model with the stratification factors (duration of symptoms and vaccination status) as covariates. The hazard ratio, p-value, 95% confidence interval (CI) for the hazard ratio from the Cox model, and proportion of COVID-19-related hospitalization or all-cause death at Day 29 from the Kaplan-Meier estimate will be provided. In addition, the p-value from stratified log rank test will be provided. If 5 events or fewer across both treatment groups are observed within 1 or more stratum, the primary endpoint will be evaluated in the same analysis described above without using the corresponding stratification factor(s) as covariates.

If a participant prematurely discontinues from the study prior to Day 29 and prior to COVID-19-related hospitalization and is alive by Day 29, or the hospitalization status is missing, the participant is censored at the Last Study Date or Day 29, whichever is earlier. If a participant prematurely discontinues from the study prior to Day 29 and prior to COVID-19-related hospitalization and then dies on or prior to Day 29, then date of the death and status will be used for the primary analysis for this participant. If a participant has a COVID-19–related

hospitalization first and then dies, then date of the COVID-19–related hospitalization and status will be used for the primary analysis for this participant. If a participant has a non COVID-19-related hospitalization first and then dies without experiencing a COVID-19-related hospitalization, then date of the death and status will be used for the primary analysis for this participant. Handling of intercurrent events is defined in Section 6.4.

The number and percentage of participants with COVID-19–related hospitalization or all-cause death by Day 29 will be summarized.

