6.5. Changes From Protocol-Specified Efficacy Analyses

An interim analysis of safety, futility and efficacy was planned in the protocol using the O'Brien-Fleming approach when 50% (1150 participants) of planned participants completed the Day 29 assessment or prematurely discontinued from the study. The second DMC meeting was to include review of the interim analysis results. Due to early stopping of enrollment of this study, the planned interim analysis was not conducted. The second and any following DMC meeting were not held.

The primary analysis set for efficacy analyses was specified as the FAS in the protocol, but will be the FAPS per FDA feedback.

The secondary endpoints of all-cause hospitalization by Day 29 and COVID-19–related MAVs by Day 29 were to be analyzed using a competing risk analysis approach, with death as the competing risk as described in the protocol. Competing risk analysis approach will not be used due to very low event rate for deaths.

Sensitivity analyses for the primary endpoint that were specified in the protocol will not be conducted.

The questionnaires to assess the impact on work productivity, activities of daily living, and functionality, WPAI + CIQ: COVID-19 and PROMIS-29, were not available to any participants by the time of stop of enrollment. Data for these questionnaires were not collected and statistical analysis will not be conducted.

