- k At screening, a urine pregnancy test will be performed at the local laboratory for participants assigned female at birth and of childbearing potential. On Day 1, Day 15, and ED visits, these participants will have a serum pregnancy test performed via the central laboratory for in-person visits or a urine pregnancy test for virtual visits. At screening, a follicle-stimulating hormone test is required to confirm the postmenopausal state in participants younger than 54 years, who have stopped menstruating for at least 12 months but do not have documentation of ovarian hormonal failure, as described in Appendix 11.3 of the protocol.
- 1 A mid-turbinate nasal swab will be collected at in-person visits and used for SARS-CoV-2 RT-qPCR, potential multiplex viral PCR, potential infectious viral titer assessment, and potential resistance testing. The nasal swab must be collected by clinic/study personnel in person. For virtual visits on Days 3, 10, or 15 no samples will be collected.
- o Medically attended visit information includes any interactions with health care professionals other than study staff or designees including hospitalization; in-person emergency, urgent, or primary care visits; or any other in-person visit attended by the participant and a health care professional. The nature and cause of the visit should be identified. Medically attended visit information and oxygen supplementation information should be collected through Day 29.
- p The COVID-19 symptom questionnaire should be completed daily (at approximately the same time each day) from predose (prior to first dose on Day 1) through Day 15, and on Day 29. If a participant discontinues from the study early, the participant should complete this questionnaire during the early discontinuation visit.
- q Study drug bottle should be returned by the participant on Day 5, if the participant has already completed both doses of study drug. If the participant has study drug at the end of the Day 5 visit, the participant may return the study drug bottle on Day 10. If the Day 10 visit is virtual, drug accountability should be performed virtually and the participant will be instructed on returning the study drug bottle.

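### When hospitalization status is missing, the primary analysis censors at a general last-contact date that can fall after hospitalization was last ascertained; the bias is small and cheap to remove

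*SAP*

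**What the plan says.** SAP 6.1.1 builds the primary endpoint from what sites report: "The endpoint will be derived by combining the available all-cause death and" COVID-19-related hospitalization. Hospitalization is captured as MAV information, reviewed at every visit after screening; the schedule in SAP Appendix 1 adds "Medically attended visit information and oxygen supplementation information should be collected through Day 29".

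SAP 6.1.3 sets the censoring date. The rule first names survivors who leave early with no such admission recorded; the sentence then goes on: "or the hospitalization status is missing, the participant is censored at the Last Study Date or Day 29, whichever is earlier". SAP 3.6.1 gives a similar rule, worded for early leavers only: "Participants with missing outcomes for the primary endpoint due to premature discontinuation from the study will be censored at the Last Study Date".

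SAP 3.8.1 defines the date: "Last Study Date is the latest of the study drug start dates and end dates, the in-person or virtual visit dates", then vital sign dates, then "the questionnaire collection dates, the laboratory collection dates, and the death date", the last applying to deaths on study. The date of the last MAV review is not named. The diary is the SIC questionnaire, which SAP 3.8.2 says "will be completed daily from predose at Day 1 to Day 15 visit, then at Day 29 visit". The form in SAP Appendix 2 has no hospitalization item.

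SAP 6.2.1 analyses the key secondary endpoints in the same way as the primary, so the hospitalization and MAV endpoints inherit the rule.

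**The concern.** Censoring at a date is sound when the participant is known to have been event-free up to that date. Here the date shows only that some contact took place. If a diary entry, or a visit with a blank MAV item, is the latest contact, the interval since hospitalization was last ascertained enters the risk set as event-free time although the outcome in it is unknown.

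The SAP is stricter elsewhere. For time to symptom alleviation, Appendix 3 censors early leavers at their last SIC assessment, a date specific to that endpoint. For the Fisher test of death, SAP 6.2.1 leaves out early leavers whose death status is missing.

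At stake are the Kaplan-Meier proportions and, if missing status differs by arm, the hazard ratio. A reader of the results would also find it hard to judge the extent. Protocol 8.5.1 planned a summary of reasons for missing data, and the matching sentence in SAP 6.1.3 omits it.

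**Working it through.** **Inputs.** The design rates in SAP 1.3 are 2% on placebo and a ratio of 0.25, so 0.5% on GS-5245, with 2300 participants randomized 1:1. Enrolment stopped below half of plan (SAP 2.3), so at most 1149. The documents give no rate of missing status; the shares m below are assumptions.

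**Plan's own figure.** The pooled two-proportion formula with 1150 per arm gives z = (0.015 × √1150 − 1.96 × √(2 × 0.0125 × 0.9875)) / √(0.02 × 0.98 + 0.005 × 0.995) = 1.28, or 90.0% power. This agrees with SAP 1.3. The figure only sets the scale; the point does not depend on it. At these rates, 1149 participants give 1149/2 × (0.02 + 0.005) = 14.4 expected events.

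**Which dates can outrun ascertainment.**

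| Component of Last Study Date | Relation to MAV review |
|---|---|
| In-person or virtual visit | MAV review is scheduled at the visit; a gap arises only if the item is blank |
| Vital signs, laboratory | Taken at in-person visits, so the same |
| Study drug dates | End around Day 5 or 6, near the Day 5 visit |
| SIC diary | Daily to Day 15, then Day 29, independent of MAV review |

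The excess therefore comes mainly from diary dates up to Day 15, or from a visit without MAV data. At Day 29 the latter credits the whole period.

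**Kaplan-Meier proportion, largest case at average risk.** Suppose a share m is never ascertained but carried to Day 29. The reported proportion is p(1 − m).
- m = 1%: 2% × 0.99 = 1.98%.
- m = 5%: 2% × 0.95 = 1.90%.

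The relative understatement is m.

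**Diary case.** Take the last MAV review at Day 5 and diary entries to Day 15. The unascertained stretch is 10 of 29 days. With a flat hazard (an assumption), the relative understatement is about m × 10/29 = 0.34m, or 1.7% at m = 5%. A hazard concentrated in those days would raise it towards m.

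**Hazard ratio.** With equal m, the ratio is 0.005(1 − m) / [0.02(1 − m)] = 0.25, unchanged. With 6% missing in one arm and 3% in the other, at average risk, the ratio is multiplied by 0.94/0.97 = 0.969, or −0.031 on the log scale. Expected events at just under half enrolment, about 2.9 and 11.5, round to 3 and 12. The standard error of the log ratio is then about √(1/3 + 1/12) = 0.65, so the shift is about 0.05 standard errors.

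**What re-dating cannot do.** Suppose, arbitrarily, that 3% are missing and have 5 times the average risk. The true rate relative to the ascertained group is 0.97 + 0.03 × 5 = 1.12.
- Carried to Day 29 as event-free: 0.97/1.12 = 0.866, 13.4% too low.
- Their unascertained time removed: 1/1.12 = 0.893, 10.7% too low.

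Re-dating recovers 2.7 of the 13.4 points. The rest is informative missingness.

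**The case against.** The strongest reply is that most of the listed dates are ascertainment dates by schedule. MAV review is due on Days 1, 3, 5, 10, 15 and 29 and at early discontinuation. The Day 29 visit may be virtual, so attending it with the MAV item blank should be unusual. Read with SAP 3.6.1, the missing-status clause may cover only early leavers, and the Day 29 case then largely disappears. There is also a second channel. In-patient hospitalization is a serious adverse event (Protocol 7.1.2), to be transmitted within 24 hours of the investigator's knowledge (Protocol 7.4.1.1), and a missed visit triggers at least three contact attempts (Protocol 3.3.3). SAP 4.1 summarizes early discontinuation with reasons.

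This narrows the point but does not remove it. The diary can still extend the date, and none of these steps makes the censoring date one on which status was known.

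Stronger readings are tempting. A reader might infer that missing status is simply imputed as not hospitalized. It is not: time after Last Study Date is censored, so full credit arises only when that date reaches Day 29. A reader might also take the 13.4% as the cost of the rule, but it rests on an assumed fivefold risk and is mostly informative missingness. Finally, with 3 against 12 events in 575 per arm, counting two missing participants per arm as events moves Fisher's p from 0.034 to 0.061. That is a worst-case bound on assumed counts and says nothing about the choice of censoring date.

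**Conclusion.** The point holds as a minor one. Followed as written, SAP 6.1.3 and 3.8.1 can place unascertained time in the risk set for the primary endpoint and for the hospitalization and MAV secondary endpoints. The direct effect is a slight understatement of the Kaplan-Meier proportions, at most about the share with missing status if their risk is average. The hazard ratio is almost unaffected when missingness is similar and uninformative in both arms, and the shift in the 6% against 3% example is far below sampling error.

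The true size is unknown because no rate of missing status is given. If missing status is linked to illness, the bias could be larger, but an earlier censoring date would remove only a small part of it. That residual risk is what the two missing-status analyses in Protocol 8.5.1 would address: multiple imputation, and counting missing as hospitalized. They were optional there, and SAP 6.5 withdraws them openly but without a reason: "Sensitivity analyses for the primary endpoint that were specified in the protocol will not be conducted".

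**What to change.** For the primary endpoint and the hospitalization and MAV secondary endpoints, replace Last Study Date in the censoring rule by the last date on which hospitalization or MAV status was actually ascertained: a completed MAV review, an adverse event or serious adverse event review, or a hospital record. Cap it at Day 29. Keep the SAP 6.1.3 rule that a death by Day 29 counts as an event even after discontinuation. State whether the missing-status clause applies to all participants or only to early leavers. Report by arm, with reasons, the number whose ascertainment ends before Day 29.

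The cost is one derived date from data already scheduled for collection, a short table and slightly less person-time. SAP 1 already provides for documenting changes made after finalization in the clinical study report. Whether to reinstate the Protocol 8.5.1 sensitivity analyses is a separate decision; the new table would show how much depends on it.

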6.2. Secondary Endpoints

Key Secondary Efficacy Endpoints

The alpha-controlled secondary endpoints include the following:

- Proportion of participants with all-cause hospitalization by Day 29
- Proportion of participants with COVID-19–related MAVs or all-cause death by Day 29
- Proportion of participants with COVID-19-related MAVs by Day 29
- Proportion of participants with all-cause death by Day 29

Medically attended visits are defined as any interactions with health care professionals other than study staff or designees including hospitalization; in-person emergency, urgent, or primary care visits; or any other in-person visit attended by the participant and a health care professional.

Other Secondary Efficacy Endpoints

- Time to COVID-19 symptom alleviation by Day 15
- Change from baseline (Day 1) in SARS-CoV-2 nasal swab viral load at Day 5

Symptom alleviation is defined as all targeted symptoms measured via the SIC questionnaire (Appendix 2) with a rating of 0, or at least 3 points decrease in rating from baseline, or an answer "No" to the question for at least 48 consecutive hours. A new version of the questionnaire that measures COVID-19 symptoms, COVID-19 Symptom Questionnaire, was introduced in protocol Amendment 1 but was not available to any participant by the time of stop of enrollment. Data for the COVID-19 Symptom Questionnaire were not collected.

Targeted symptoms are those listed below:

- Nasal congestion (stuffy nose)
- Runny nose
- Sore throat

- Shortness of breath (difficulty breathing)
- Cough
- Feeling generally unwell (run down)
- Fatigue (tiredness)
- Physical weakness
- Feeling faint
- Muscle aches/pains
- Joint aches/pains
- Headache
- Chills
- Uncontrollable body shaking/shivering
- Fever

The first day of the 48 consecutive hours will be considered the symptom alleviation date. The date and time stamps at which participants complete the questionnaire each day are captured in electronic diary as "Form Saved Time" and will be used to determine whether the requirement of 48 continuous hours is satisfied.

A potential symptom alleviation is identified first and defined as all targeted symptoms with a rating of 0, or at least 3 points decrease in rating from baseline, or an answer "No" to the question, ie, without 48 consecutive hours confirmation. For participants with missing baseline symptoms data, all targeted symptoms need to have either a rating of 0 or an answer "No" to the question to be considered as potential symptom alleviation.

If there is any intercurrent event prior to Day 15 and prior to the time a participant achieves symptom alleviation, it will be handled per Section 6.4.

As the questionnaire recall time is the previous 24 hours, an additional consecutive 24 hour period is needed to achieve 48 consecutive hours of symptom alleviation. The duration for the second consecutive 24 hours is calculated as shown in the flowchart:

No missing day is allowed between first date and last date of potential symptom alleviation included in the calculation.

The date-time of the first potential alleviation will be considered as the date-time of symptom alleviation and will be used for the calculation of time to symptom alleviation. Otherwise, repeat the algorithm for the next potential symptom alleviation time.

Details and examples of algorithm for symptom alleviation are provided in Appendix 3.

